### **4.3.1 SALT and ALODEX Scores**

For both SALT and ALODEX the mean and mean change from baseline will be tabulated by visit and treatment group. Change will be assessed both as an absolute percentage difference (timepoint percentage score – baseline percentage score) as well as relative percent regrowth (absolute percentage difference divided by baseline percentage \* -1). In addition, the proportion of patients that have  $\geq 25\%$ ,  $\geq 50\%$  and  $\geq 75\%$  regrowth will be tabulated for both SALT and ALODEX.

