Study Design: During the double-blind period, this Phase 2, multicenter, randomized study is designed to evaluate the safety, tolerability, pharmacokinetics and pharmacodynamics of ATI-50002 Topical Solution in subjects with AU and AT. Subjects will be required to have a clinical diagnosis of stable, clinically typical, AU or AT for a duration of at least 6 months up to and including seven years. In the double-blind phase, a total of approximately 12 subjects will be randomized to a 2:1 ratio: 
 • ATI-50002 Topical Solution, 0.46%, BID for 28 days (8 subjects) • Vehicle Solution BID for 28 days (4 subjects) During the screening period, subjects will be assessed for eligibility into the study. Subjects who meet all the entry criteria will be randomized to ATI-50002 Topical Solution, 0.46% or Vehicle Topical Solution and will apply a minimum of 1.5 mLs up to a maximum of 4 mLs of study medication to the entire scalp twice-a-day (BID) for 28 days (except for Day 1 and Day 28 when study medication will only be applied once a day). For the first 6 subjects enrolled in the study, blood samples for concentrations of ATI-50002 will be collected on Day 1 (Visit 2) and Day 28 (Visit 6) at pre-dose and 1, 2, 4, 8 hours post dose and on Day 2 (Visit 3) and Day 29 (Visit 7) at 24 hours post-dose. Blood samples for immunology will be collected on Day 1 (Visit 2) before study medication application and on Day 29 (Visit 7), 24 hours after study medication application on Day 28 (Visit 6). A 4-mm punch biopsy of the scalp will be obtained to determine the concentration of ATI-50002 in the scalp skin on Day 2 (Visit 3) and on Day 29 (Visit 7) 24 hours after study medication application on Day 1 (Visit 2) and on Day 28 (Visit 6). A 4-mm punch biopsy will be obtained to determine histology and immunology, prior to study medication application on Day 1 (Visit 2) and on Day 29 (Visit 7), 24 hours after study medication application on Day 28 (Visit 6). Safety and tolerability will be evaluated	

at each study visit by assessment of adverse events and vital signs, and at select visits, ECGs and clinical laboratory tests will be completed.

Open-Label Extension:

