6.7. Replacement Subjects

Subject enrollment will continue until approximately 12 subjects have been randomized. Subjects who are randomized and do not complete the study will not be replaced.

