6.8. Subject Withdrawal Criteria

Subjects will be informed that they are free to withdraw from the study at any time and for any reason. The Investigator may remove a subject from the study if, in the Investigator's opinion, it is not in the best interest of the subject to continue the study. Examples of other reasons subjects may be discontinued from the study are: a change in compliance with an inclusion or exclusion criterion, occurrence of AEs, occurrence of pregnancy or use of a prohibited therapy. The Investigator or designee must inform the Aclaris Therapeutics, Inc. study monitor of any subject discontinuation. (Refer to Section 10.2.4 for study medication discontinuation or termination criteria).

In case of premature discontinuation of study participation, all efforts will be made to perform all Week 56 (Visit 16) assessments. The date the subject is withdrawn from the study and the reason for discontinuation must be recorded in the subject's electronic case report forms (eCRFs). All withdrawn subjects with ongoing AEs will be followed until the event has resolved or stabilized, until the subject is referred to the care of a local health care professional, or until a determination of a cause unrelated to the study medication or study procedures is made.

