12.5.4. Secondary Analyses

Summary descriptive statistics (N, mean, median, SD) by visit will be provided for all efficacy parameters. Secondary efficacy parameters are described below:

The secondary efficacy endpoints include mean change from baseline in the SALT score at Week 28 (Visit 13), Week 40 (Visit 14) and Week 52 (Visit 15).

The percentage hair growth will be calculated as the mean change from Baseline (Visit 2) scores compared to end of treatment Week 28 (Visit 13), Week 40 (Visit 14) and Week 52 (Visit 15).

Mean change from baseline in the ALODEX score, proportion of subjects achieving a $\geq 50\%$ hair growth compared with baseline.

Treatment satisfaction will be summarized.

The ALODEX score analysis will use the same methodology as specified for SALT score analysis. Other parameters will be analyzed as detailed in the statistical analysis plan.

Mean change from baseline in eyebrow growth will be calculated as the mean change in the Clinician’s Eyebrow Assessment (CEA) from entry into the long-term, open-label extension compared to Week 28(Visit 13), Week 40 (Visit 14) and Week 52 (Visit 15). The CEA evaluates eyebrows on a scale from “No eyebrow hair” (Grade 0) to “Full eyebrow hair” (Grade 4).

Mean change from baseline in the Subject's Eyebrow Assessment (SEA) will be calculated from entry into the long-term open label extension to Week 28 (Visit 13), Week 40 (Visit 14) and Week 52 (Visit 15). The SEA evaluates eyebrows on a scale from "No eyebrow hair" (Grade 0) to "Full eyebrow hair" (Grade 4).

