## 4. STATISTICAL METHODS

In general summaries will be presented according to double-blind treatment group and additionally for the subset of patients entering open-label. Other than baseline data (ie data collected prior to the first application of double-blind medication), the data summarized corresponds to the period of collection (ie during double-blind or during open-label). For those entering open-label, the open label period begins at the application of open-label medication. Additional details are provided in the data handling and programming specifications document. No imputation of missing data was performed other than completely or partially missing dates as described in the Data Handling and Programming Specifications document.

All Data listings are sorted by double-blind treatment group and patient ID.

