#### **4.7 Sample Size**

Since this is the first multicenter study of ATI-50002 Topical Solution in subjects with stable alopecia universalis and alopecia totalis, sample size considerations were based upon feasibility factors and not on a formal power computation.

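### Open-label regrowth proportions at Weeks 28, 40 and 52 are observed-case with no all-entrant denominator, so they will be overstated if non-responders leave

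*SAP*

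**What the plan says.** - **Summaries.** In SAP 4.3.1 (SALT and ALODEX Scores), the "mean and mean change from baseline will be tabulated by visit and treatment group". A further sentence adds "the proportion of patients that have" at least 25%, 50% and 75% regrowth. That sentence names neither a visit nor a denominator.
- **Missing data.** SAP section 4: "No imputation of missing data was performed other than completely or partially missing dates".
- **Timepoints.** Protocol 12.5.4 sets the SALT change at Weeks 28, 40 and 52 (Visits 13, 14 and 15) and applies the same method to ALODEX. Week 56 is not among them.
- **Analysis set.** SAP 4.1.1 uses the As-Treated population (at least one application) for pharmacodynamic analyses, and SAP 4.3 places SALT and ALODEX under that heading. This decides who belongs to the set. It does not decide who counts at a visit they did not attend.
- **Leavers.** Protocol 6.7: "Subjects who are randomized and do not complete the study will not be replaced". For early discontinuation, protocol 6.8 says "all efforts will be made to perform all Week 56 (Visit 16) assessments", and the schedule in protocol 7.3 includes SALT and ALODEX at Visit 16.
- **Two versions of the extension.** Protocol 7.1 requires subjects who entered the 6-month extension under Amendment 1 to re-consent before continuing for a further 6 months.

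**The concern.** Counting a missed visit as non-response is a form of imputation. Read with the no-imputation rule, the proportions can therefore only be observed-case: responders among those still attending.

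The protocol's own expectations make selective departure plausible. The synopsis expects early vellus regrowth to take at least 3 to 6 months and measurable terminal regrowth at least 6 months, so a subject who leaves early will usually leave with little regrowth. The re-consent step comes at about 6 months of open-label treatment, when subjects can see whether treatment has worked and just before the Week 40 and 52 summaries. With no concurrent control arm, a shrinking denominator can look like late response. What is at stake is the main description of efficacy from the extension. No hypothesis test is affected, because none is planned.

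**Working it through.** **The plan's own figures.** There is no power, response-rate or dropout figure to reproduce. SAP 4.7 says "sample size considerations were based upon feasibility factors and not on a formal power computation". The only arithmetic is the allocation: "a total of approximately 12 subjects will be randomized to a 2:1 ratio", which gives 12 × 2/3 = 8 active and 12 × 1/3 = 4 vehicle, as stated.

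**Inputs, all assumed.** N = subjects entering open-label (12 at most; 8 if only the original active group is tabulated). R = responders, all of whom stay. d = non-responders who leave before the visit.

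**Formulas.** Observed-case = R/(N − d). All-entrant, missing as non-response = R/N. Their ratio is N/(N − d), whatever R is. For N = 12 it is 1.2 at d = 2, 1.5 at d = 4 and 2.0 at d = 6.

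| N | R | d | Observed-case | All-entrant | Difference (points) |
|---|---|---|---|---|---|
| 12 | 2 | 0 | 2/12 = 16.7% | 16.7% | 0 |
| 12 | 2 | 2 | 2/10 = 20.0% | 16.7% | 3.3 |
| 12 | 2 | 4 | 2/8 = 25.0% | 16.7% | 8.3 |
| 12 | 2 | 6 | 2/6 = 33.3% | 16.7% | 16.7 |
| 12 | 3 | 4 | 3/8 = 37.5% | 25.0% | 12.5 |
| 12 | 3 | 6 | 3/6 = 50.0% | 25.0% | 25.0 |
| 8 | 2 | 4 | 2/4 = 50.0% | 25.0% | 25.0 |

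**Precision.** Exact (Clopper-Pearson) 95% intervals are 3% to 65% for 2/8 and 2% to 48% for 2/12.

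**Means.** Assume 3 responders with 60% regrowth and 9 subjects with none. Over all 12 the mean is 180/12 = 15.0%. Observed-case it is 180/10 = 18.0% at d = 2, 180/8 = 22.5% at d = 4 and 180/6 = 30.0% at d = 6.

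**Direction, with N = 12 and 3 true responders (25%).**
- Four leave at random. The expected number of responders remaining is 3 × 8/12 = 2. Observed-case is 2/8 = 25%, so no expected bias. Counting missing as non-response gives 2/12 = 16.7%, which is too low.
- One responder leaves. Observed-case is 2/11 = 18.2%, an understatement.

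Overstatement therefore requires that non-responders leave more readily than responders. The all-entrant figure is conservative rather than unbiased, which is why both are needed.

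**The 6-month completers.** Suppose 2 of the 4 leavers in the 2/8 case had finished the 6-month extension and not re-consented. At Week 40, setting those two aside gives 2/10 = 20.0%, between 16.7% and 25.0%.

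**The case against.** The strongest reply is that this is a missing denominator statement in a descriptive secondary analysis of at most 12 subjects. The intervals above overlap almost entirely. Attrition will be visible: protocol 12.5.4 promises N by visit for the efficacy parameters, and SAP 4.1.2 reports disposition with reasons for discontinuation. Selective dropout is plausible but undocumented. All of this stands, and it limits the importance of the point. It does not tell a reader what the response rate is among everyone who started open-label treatment.

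A simple non-response rule would also be unfair to subjects who entered a 6-month extension, completed it and did not re-consent. Weeks 40 and 52 lay outside the extension they joined. That objection is right, and the fix allows for it. Non-response counting also does nothing for the mean changes, for which n per visit is the practical safeguard.

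A reader might go further and infer that leavers' exit scores are tabulated as Week 56, so that this row mixes treatment durations and also takes in the Day 59 visit of subjects who never continued. The documents do not support that:
- Protocol 6.8 says which assessments to perform at exit, not under which visit the scores are analysed.
- SAP section 4 refers further detail to a Data Handling and Programming Specifications document, which is not available here and may contain visit mapping.
- SAP section 4 summarises data by period of collection, which largely separates non-continuers from open-label data. SAP 4.4.4 applies that logic explicitly to ECG follow-up.
- Week 56 is not an efficacy timepoint, and scores from earlier scheduled visits stay where they are.

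**Conclusion.** The point holds in conditional form. As written, the SAP gives observed-case regrowth proportions, and these overstate open-label response at Weeks 28, 40 and 52 if non-responders leave. For the proportions, observed-case is a deduction from the no-imputation rule and the absent denominator, since SAP 4.3.1 does not use the term. Placing them at those three weeks relies on the protocol's timepoints.

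The size cannot be fixed from the documents. With 12 assumed entrants and 2 responders, the excess is 3.3 points if 2 non-responders leave, 8.3 points if 4 leave and 16.7 points if 6 leave. It would be wrong to conclude that response will be overstated whatever happens: under dropout unrelated to response the expected bias is nil, and if responders leave it reverses. This is a worthwhile, inexpensive correction to a descriptive analysis and not a threat to the trial's primary objective.

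**What to change.** In SAP 4.3.1 (SALT and ALODEX Scores):

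1. Report the 25%, 50% and 75% regrowth proportions at Weeks 28, 40 and 52 over all subjects with at least one open-label application, with missing counted as non-response. Put them next to the observed-case proportions and means, with n at each visit.
2. Show separately the subjects who completed the original 6-month extension and did not re-consent. In at least one presentation, do not count them as failures at Weeks 40 and 52.
3. Unless the Data Handling and Programming Specifications already do so, assign an early-exit SALT or ALODEX score collected as Visit 16 to a scheduled visit by a stated OLE-day window, and only when that visit has no score. For example, an exit at OLE Day 260 should not displace a Visit 14 score from OLE Day 252.
4. Limit any Week 56 row to subjects seen at OLE Day 364 ± 7.

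The cost is a few sentences, one extra table and possibly lower response figures. No new data are needed.

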### **4.3.1 ALADIN Scores**

The analysis of ALADIN scores will be detailed in a separate document.

### **4.3.2 Eyebrow Assessments during Open-Label**

For patients entering open-label, mean Percent hair loss, CEA and SEA scores mean and mean change from baseline will be provided by visit. At entry into open-label, V7, summary statistics will be provided by double-blind treatment group as well as for all patients entering open-label. Where applicable, each patient's scores for the left and right eyebrows will be averaged prior to summarization. Individual scores for the left and right eyebrows will be provided in the data listings.

### **4.3.3 Subject Global Impression of Treatment Satisfaction (SGIS)**

For patients entering open-label, descriptive statistics (N, mean, SD, median, minimum

and maximum) of the SGIS will be provided by visit. Additionally, the number of percentage of patients recording each of the 7 possible SGIS scores will be provided categorically.

#### **4.4 Safety Analyses**

The comprehensive safety analysis is based on all patients in the AS population.

The following sections detail the summaries performed on the safety data. Additional data handling rules including those for imputation of partially missing dates are provided in a separate SAP document pertaining to data handling and programming specifications.

The baseline scores for vital signs, laboratory assessments and ECGs will be the last non-missing value collected  $\leq$  the date of the first application of double-blind study medication. This baseline will be used also for calculating changes during open-label for these variables.

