9.5.5. ECGs

Standard 12-lead ECGs will be performed by a qualified staff member at Screening (Visit 1), Baseline (Visit 2), Day 15 (Visit 5), Day 29 (Visit 7) and the visits outlined in Section 7.3. The ECGs must be obtained using a standard 12-lead ECG with a 10mm/mV amplitude, at 25mm/sec and a 5-10-second duration. To ensure a steady heart rate the subject must rest quietly in the supine position for at least 5 minutes prior to performing the ECG.

A central lab, eResearchTechnology, Inc. (ERT), will provide equipment, supplies and site training. In addition, ERT will process ECGs received by the sites and report results via a secure study portal. The ECG results will be interpreted by a qualified health professional (evaluator) and

the interpretation reported either directly on the tracing or in a separate report. The evaluator will interpret the results of every ECG and define the ECG as “normal” or “abnormal”. Variations such as minor ST changes (*i.e.*, <0.5mm depression) and early re-polarization are considered normal.

The investigator must review the evaluator’s interpretation of each subject’s screening ECG prior to Baseline (Visit 2). The investigator will review the evaluator’s interpretation of all ECG reports in a timely manner and comment on the clinical relevance of any result that is defined by the evaluator as abnormal.

Any abnormalities that are, in the opinion of the investigator, clinically significant, must be reported as medical history if found prior to the start of the first study medication application or as an AE if found after the start of the first study medication application (see Section 10.1.1).

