## **4.3 Pharmacodynamic Endpoints**

The baseline scores for SALT and ALODEX will be the last non-missing value collected  $\leq$  the date of the first application of double-blind study medication. This baseline will be used also for calculating changes during open-label for these variables. For the eyebrow assessments (CEA and SEA), the value collected at V7 will be used as the baseline for calculating changes during subsequent visits.

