#### **4.4.4 ECG assessments**

The core laboratory's interpretation of the ECGs are summarized as "shift" from baseline to "worst" overall interpretation recorded after baseline where the order of severity of the interpretations from best to worst are "Normal", "Abnormal, NCS" and "Abnormal, CS". Separate summaries are used for post baseline data collected during double-blind and during open-label. If applicable, follow-up visits are included in the post-baseline data dependent upon entry into open-label (ie included in double-blind assessment if a patient did not enter open-label and in open-label assessment if they did).

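### For vehicle-randomised subjects, SAP 4.4 counts laboratory, vital-sign and ECG change that arose on vehicle as change during open-label ATI-50002

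*SAP*

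**What the plan says.** SAP 4.4 defines one safety baseline: "The baseline scores for vital signs, laboratory assessments and ECGs will be the last non-missing value collected" on or before the date of the first double-blind application. The next sentence carries it into the extension: "This baseline will be used also for calculating changes during open-label for these variables". Neither sentence separates vehicle-randomised from ATI-50002-randomised subjects.

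Sections 4.4.3 and 4.4.5 then summarise change from baseline by visit for vital signs, chemistry and hematology. Section 4.4.5 also tabulates laboratory shifts from baseline to the worst later value. Section 4.4.4 does the same for ECG interpretations, by period: "Separate summaries are used for post baseline data collected during double-blind and during open-label".

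SAP section 4 fixes the boundary between periods: "For those entering open-label, the open label period begins at the application of open-label medication". On grouping it says: "In general summaries will be presented according to double-blind treatment group and additionally for the subset of patients entering open-label".

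Two other kinds of data are handled differently. For the eyebrow scores (CEA and SEA), SAP 4.3 says that "the value collected at V7 will be used as the baseline for calculating changes during subsequent visits". Adverse events are assigned to a period by onset date (SAP 4.4.1).

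Under the protocol, about 12 subjects are randomised 2:1 (8 to ATI-50002, 4 to vehicle) for 28 days, and everyone in the extension applies ATI-50002.

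**The concern.** A baseline should sit immediately before the exposure whose effect is being described. For a subject randomised to ATI-50002 with no gap, the value before the double-blind period does that, and open-label change from it describes total time on drug. For a subject randomised to vehicle it does not: the interval to any open-label visit begins with the whole vehicle period.

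Splitting the data by period of collection does not solve this. It decides which post-baseline values enter a table, but not what they are compared with. A laboratory value that leaves the normal range on vehicle and stays out is a shift in the vehicle table and also in the open-label table.

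Safety and tolerability belong to the primary objective, and the extension supplies the trial's only ATI-50002 data beyond 28 days. With so few subjects, one misattributed shift is visible in the percentages. The tables could also disagree: an abnormality reported as an adverse event with onset on vehicle belongs to the double-blind vehicle column in SAP 4.4.1, while the same abnormality, if it persists, is an open-label shift under SAP 4.4.4 or 4.4.5.

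**Working it through.** The plan has no power, alpha or effect figure to reproduce; the sample size rests on feasibility (SAP 4.7).

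**Inputs**
- Allocation: 12 subjects at 2:1 gives 8 + 4, as the protocol synopsis states.
- Schedule (protocol 7.3): the treatment day minus the OLE day is 29 at every visit from Visit 8 to Visit 16, so with no gap open-label starts on Day 29. That is 28 days after Day 1. The Visit 7 window allows up to three days fewer.
- Open-label laboratory tests: Visits 9, 13, 14, 15 and 16. Open-label ECGs: Visits 9, 13 and 16. Vital signs: every visit.
- Last scheduled value before open-label: Visit 7 for all three. For ECG, protocol 9.5.5 lists "Day 15 (Visit 5), Day 29 (Visit 7) and the visits outlined in Section 7.3".
- Gap length: not given. A range of 30 to 90 days is assumed below.

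**Step 1: share of the interval that precedes ATI-50002 in a former vehicle subject**

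Share = (28 + gap) / (28 + gap + OLE day).

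| Visit | OLE day | No gap | Gap 30 days | Gap 90 days |
|---|---|---|---|---|
| 9 | 56 | 28/84 = 33% | 58/114 = 51% | 118/174 = 68% |
| 13 | 168 | 28/196 = 14% | 58/226 = 26% | 118/286 = 41% |
| 15 | 336 | 28/364 = 8% | 58/394 = 15% | 118/454 = 26% |

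The share is largest at Visit 9, the first open-label laboratory test and ECG. For vital signs at Visit 8 it is 28/56 = 50% with no gap.

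**Step 2: trace one persistent change**

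Take a vehicle subject whose ECG is normal at baseline, abnormal but not clinically significant at Visit 7, and unchanged at Visit 9.
- Double-blind table: normal to abnormal, one shift on vehicle.
- Open-label table under SAP 4.4: normal to abnormal, one shift on ATI-50002.
- Open-label table from Visit 7: abnormal to abnormal, no shift.

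**Step 3: weight in the open-label column**

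With A former active and V former vehicle subjects entering, one carried-over shift adds 1/(A + V). A mean drift d among the former vehicle subjects moves the pooled mean by d × V/(A + V).
- All enter (8 + 4): 1/12 = 8.3 points per shift, and d × 4/12 = d/3.
- Former vehicle subjects shown alone: 1/4 = 25 points per shift, and the full d.
- Other entry patterns (assumed 2 to 8 active, 1 to 4 vehicle): the weight on d runs from 1/9 = 11% to 4/6 = 67%.

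**Step 4: after re-baselining**

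If the drift d arises on vehicle, persists, and nothing further happens in open-label, the change from Visit 7 is 0 in the former vehicle subjects and their contribution to the pooled mean is 0. Change during a gap remains: with a gap of 30 to 90 days it still occupies 30/86 = 35% to 90/146 = 62% of the Visit 7 to Visit 9 interval.

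**The case against.** A single pre-treatment reference is a defensible convention, and the plan gives the reader other ways to see what happened. Actual values are tabulated by visit for vital signs and laboratory tests. Listings are sorted by double-blind group and subject. If the by-group presentation in SAP section 4 carries into open-label, d/3 touches only the pooled column. Clinically significant laboratory, vital-sign and ECG abnormalities must be reported as adverse events, which go by onset date, and clinically significant adverse events bar entry to the extension. All of this stands. It means that carry-over is mostly confined to shifts that are not clinically significant. It does not correct the change and shift columns, because the laboratory shift tables count any out-of-range value and the ECG table has its own category for abnormal but not clinically significant.

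Three stronger readings are tempting, and the documents do not support them.

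- *That the open-label summaries as a whole are not changes on ATI-50002.* Eight of the 12 planned subjects are on ATI-50002 from Day 1. With no gap, vehicle time is 14% of the interval at Visit 13 and 8% at Visit 15, and only in former vehicle subjects.
- *That a Visit 7 baseline also removes change in an administrative gap.* Visit 7 precedes the gap. The delayed-entry visit (protocol 7.3, footnotes 17 and 18) lists consent, instructions, dispensing and eyebrow scores, but no laboratory tests, ECG, SALT or ALODEX.
- *That hair regrowth on vehicle is credited to the drug to any material degree.* SAP 4.3 does apply the same rule ("The baseline scores for SALT and ALODEX will be the last non-missing value collected" on or before the first double-blind application), but protocol 12.5.4 itself defines percentage hair growth from Visit 2. The protocol does not anticipate regrowth within 28 days and calls spontaneous regrowth rare in AT and AU. Entry requires more than 95% scalp hair loss, so SALT can worsen by less than 5 points, or less than 5 × 4/12 = 1.7 points in a pooled mean.

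**Conclusion.** The point holds for laboratory, vital-sign and ECG change and shift summaries in vehicle-randomised subjects. In these subjects the open-label change includes the planned 28 vehicle days plus any gap, and a change that persists is reported twice, once under vehicle and once under open-label ATI-50002. The SAP already avoids this for eyebrow scores and adverse events, which are unaffected.

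The size is 8.3 percentage points per carried-over shift and d/3 for a mean, assuming that all 12 subjects enter and that results are pooled. These figures show sensitivity and do not predict a bias: the documents give neither d nor the number of persistent shifts. Only changes still present at an open-label visit carry over. No test or error rate is involved, so the matter is one of attribution in descriptive tables. It is worth correcting because the correction is cheap.

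**What to change.** In SAP 4.4, add that for vehicle-randomised subjects the baseline for open-label laboratory, vital-sign and ECG change and shift summaries is the last non-missing value before the first open-label application, normally Visit 7. Visit 7 values taken on the day open-label medication is started should count as before it. Keep the current baseline for ATI-50002-randomised subjects and for all double-blind summaries.

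Footnote the two definitions in every affected open-label table. Footnote subjects with an administrative gap, in either randomised group, because change during the gap remains in their figures.

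For SALT and ALODEX, keep the protocol's Visit 2 baseline as the main analysis. A Visit 7-based change in former vehicle subjects could be added as a supplementary summary, with little expected effect.

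The cost is a short addition to SAP 4.4, one derived baseline flag and the footnotes. No new data are needed, since all three measures are scheduled at Visit 7. The drawback is two baseline definitions within one pooled column, which the footnotes and the by-group presentation make readable.
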